3.2. Secondary Endpoints

- Evaluate the safety and tolerability of elotuzumab in combination with KRd by monitoring AE rate, classification, and relation to study drug
- Compare rates of MRD between MFC and NGS at the end of cycles 4, 8, and 12 for all subjects, and end of C18 (for subjects who are MRD+ at the end of C8 but MRD- at the end of C12 only), 24 months after C1D1, and yearly after that.
- Estimate the time to event including duration of response (DOR), progression-free survival (PFS), time to progression (TTP), and overall survival (OS)

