8. ADVERSE EVENTS

An Adverse Event (AE) is defined as any new untoward medical occurrence or worsening of a preexisting medical condition in a clinical investigation subject administered an investigational (medicinal) product and that does not necessarily have a causal relationship with this treatment. An AE can therefore be any unfavorable and unintended sign (such as an abnormal laboratory finding), symptom, or disease temporally associated with the use of investigational product, whether or not considered related to the investigational product.

Adverse events can be spontaneously reported or elicited during open-ended questioning, examination, or evaluation of a subject. (In order to prevent reporting bias, subjects should not be questioned regarding the specific occurrence of one or more AEs.)

NONSERIOUS ADVERSE EVENT

- Nonserious Adverse Events are to be provided to BMS in aggregate via interim or final study reports as specified in the agreement or, if a regulatory requirement [e.g. IND US trial] as part of an annual reporting requirement.
- Nonserious AE information should also be collected from the start of a placebo lead-in period or other observational period intended to establish a baseline status for the subjects.

A nonserious adverse event is an AE not classified as serious.

Nonserious Adverse Event Collection and Reporting

The collection of nonserious AE information should begin at initiation of study drug. All nonserious adverse events deemed to be related to study drug combination should be collected continuously during the treatment period and for a minimum of 30 days following the last dose of study treatment.

Nonserious AEs should be followed to resolution or stabilization, or reported as SAEs if they become serious. Follow-up is also required for nonserious AEs that cause interruption or discontinuation of study drug and for those present at the end of study treatment as appropriate.

Laboratory Test Abnormalities

All laboratory test results captured as part of the study should be recorded following institutional procedures. Test results that constitute SAEs should be documented and reported as such.

The following laboratory abnormalities should be documented and reported appropriately:

- any laboratory test result that is clinically significant or meets the definition of an SAE
- any laboratory abnormality that required the subject to have study drug discontinued or interrupted

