- any laboratory abnormality that required the subject to receive specific corrective therapy.

Potential Drug Induced Liver Injury (DILI)

Wherever possible, timely confirmation of initial liver-related laboratory abnormalities should occur prior to the reporting of a potential DILI event. All occurrences of potential DILIs, meeting the defined criteria, must be reported as SAEs. Potential drug induced liver injury is defined as:

- 1) ALT or AST elevation > 3 times upper limit of normal (ULN) AND
- Total bilirubin > 2 times ULN, without initial findings of cholestasis (elevated serum alkaline phosphatase)
 AND
- 3) No other immediately apparent possible causes of AST/ALT elevation and hyperbilirubinemia, including, but not limited to, viral hepatitis, pre-existing chronic or acute liver disease, or the administration of other drug(s) known to be hepatotoxic.

Overdose

An overdose is defined as the accidental or intentional administration of any dose of a product that is considered both excessive and medically important. All occurrences of overdose must be reported as an SAE.

Other Safety Considerations

Any significant worsening noted during interim or final physical examinations, electrocardiograms, x-rays, and any other potential safety assessments, whether or not these procedures are required by the protocol, should also be recorded as a nonserious or serious AE, as appropriate, and reported accordingly.

Unexpected AEs

An unexpected AE is any adverse drug event, the specificity or severity of which is not consistent with the current IB or prescribing information for a marketed compound. Also, reports which add significant information on specificity or severity of a known, already documented AE constitute unexpected AEs. For example, an event more specific or more severe than described in the IB would be considered "unexpected".

Whenever possible, the Common Terminology Criteria for Adverse Events (CTCAE) version 4.0 should be used to describe the event and for assessing the severity of AEs (see Appendix 3). Any events representing a change in the CTCAE Grade need to be reported on the AE case report form. This includes any change in laboratory values.

For AEs not adequately addressed in the CTCAE, the severity table below may be us	For AEs r	ot adequately	addressed in	the CTCAE.	the severity	v table below may	v be used:
---	-----------	---------------	--------------	------------	--------------	-------------------	------------

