The Treating Investigator is responsible for evaluating all AEs for relationship to study drug and for seriousness, obtaining supporting documents, and determining that documentation of the event is adequate. Adverse events will be assigned a severity grade using the NCI-CTCAE grading scale v4.0. The Treating Investigator must assess all abnormal laboratory results for their clinical significance. Only grade 1 & 2 abnormal laboratory values considered clinically significant, related to study treatment, and/or requiring concomitant medication will be recorded. If any abnormal laboratory result is considered clinically significant, the Treating Investigator must provide details about the action taken with respect to the test drug and about the subject's outcome. All Grade 3 and 4 laboratory abnormalities must be recorded as AEs on the CRF. Grade 1 and 2 abnormalities should only be recorded if they require treatment or are otherwise considered clinically significant by the Treating Investigator.

The Lead Principal Investigator may delegate these duties to Sub-investigators and must ensure that these Sub-investigators are qualified to perform these duties under the supervision of the Lead Principal Investigator, and that they are listed on the delegation log.

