10.2.1. Primary Objective Sample Size Justification

The primary endpoint is the sCR rate and/or the rate of MRD-negativity after 8 cycles of therapy. The rate of sCR for KRd treatment is established as the primary reference endpoint for statistical considerations by robust data (Jakubowiak et al., 2012b) Recognizing that the measurement of sCR has technical challenges when involving elotuzumab – which are anticipated to be resolved by the time it is needed – a co-primary endpoint of MRD-negative status by NGS is included in the primary efficacy assessment. This is based on the close correlation between MRD-negative status and sCR rate established in the ongoing KRd+transplant study (Jakubowiak et al. EHA 2016, Zimmerman et al. ASH 2016, both oral presentations). This primary endpoint incorporates also the new definition of MRD status, which requires sCR to confirm MRD negativity (Kumar et al., 2016). Therefore, an improvement from historical 30% (which is the sCR rate and the estimated MRD-negative rate by NGS in the KRd study without elotuzumab (Jakubowiak, 2016)) to 50% or higher sCR and/or MRD-negative status at the completion of 8 cycles, would be considered promising.

For 40 non-transplant candidates and/or transplant candidates who agreed to defer transplant, we will test the null hypothesis that the sCR and/or negative MRD status by NGS rate after 8 cycles is, \leq 30% against the alternative that it is, \geq 30% using an exact one-sided binomial test at the alpha=0.10 significance level. The null hypothesis will be rejected if 17 or more sCR's and/or MRD-negative's responses are observed (\geq 42.5%). The sample size of n=40 response evaluable subjects provides a little over 85% power if the true sCR and/or negative MRD status rate by NGS is 50%. The sample size is selected to also allow for collection of sufficient data for toxicity and tolerability evaluation of the E-KRd regimen. The frequency of adverse events will be summarized by type, grade, and attribution to the study drugs.

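### Sections 8 and 8.2 give conflicting rules for recording Grade 1–2 laboratory changes as adverse events, so those frequencies can depend on which sentence a site follows

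*Combined protocol and SAP*

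**What the plan says.** Four pieces of text bear on whether a laboratory value becomes an AE record.

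- **Section 8, under Unexpected AEs.** "Any events representing a change in the CTCAE Grade need to be reported on the AE case report form", followed by "This includes any change in laboratory values". No grade, significance, relatedness or treatment threshold is attached.
- **Section 8.2, first sentence on low grades.** "Only grade 1 & 2 abnormal laboratory values considered clinically significant, related to study treatment, and/or requiring concomitant medication will be recorded".
- **Section 8.2, last sentence of the same paragraph.** "Grade 1 and 2 abnormalities should only be recorded if they require treatment or are otherwise considered clinically significant by the Treating Investigator". Relatedness is no longer a route in.
- **Section 8, Laboratory Test Abnormalities.** A list of three triggers, starting with "any laboratory test result that is clinically significant or meets the definition of an SAE". The other two are abnormalities that led to stopping or pausing study drug and those that needed corrective therapy.

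For higher grades 8.2 is unambiguous: "All Grade 3 and 4 laboratory abnormalities must be recorded as AEs on the CRF".

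Two places use the resulting records. The secondary safety endpoint in 3.2 is to "Evaluate the safety and tolerability of elotuzumab in combination with KRd by monitoring AE rate, classification, and relation to study drug". The analysis in 10.2.1 is: "The frequency of adverse events will be summarized by type, grade, and attribution to the study drugs".

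**The concern.** The section 8 sentence and the two sentences in 8.2 are all written as instructions to sites, and the protocol does not rank them. A coordinator who follows section 8 enters every Grade 1 or 2 laboratory shift. One who follows 8.2 enters only those that pass the investigator's filter, and which filter applies depends on the sentence read.

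At stake are the Grade 1–2 rows for cytopenias and chemistry changes in the AE tables. Section 4.2.2 plans 5 centers, treatment is open-label, and the 8.2 filters rest on the treating investigator's judgement. If centers follow different sentences, those rows add together complete and selective capture. The AE rate is itself a secondary endpoint, and 15 of the 55 subjects are enrolled to add tolerability and toxicity data (1.7, 10.2), so how toxicity is captured matters to the design.

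Whether non-serious AEs must be drug-related to be collected at all is a separate question. Settling it would not say whether an untreated, non-significant Grade 1–2 laboratory value belongs on the form.

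**Working it through.** No alpha, power or rate enters this point and the plan states no figure to reproduce. The check is to apply each rule to the same laboratory result.

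Rules:
- **A**: the section 8 sentences on grade change, read literally.
- **B**: the first low-grade sentence in 8.2, taking its and/or to mean that any one of its three conditions is enough.
- **C**: the last sentence of the same 8.2 paragraph.

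| New laboratory grade shift | A | B | C |
|---|---|---|---|
| Grade 1–2, untreated, not significant, unrelated | record | do not record | do not record |
| Grade 1–2, untreated, not significant, judged related | record | record | do not record |
| Grade 1–2, needs medication | record | record | record |
| Grade 1–2, clinically significant | record | record | record |
| Grade 3–4 | record | record (separate 8.2 sentence) | record (separate 8.2 sentence) |

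Row 1 is the conflict between sections 8 and 8.2. Row 2 is a conflict inside one paragraph of 8.2. The remaining rows agree.

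Next, does a narrower reading of A remove the problem? Suppose A covers only the regrading of events already on the AE form. A then no longer triggers a record in rows 1 and 2. Row 1 becomes consistent. Row 2 does not, because B still records and C still excludes.

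Last, what depends on rows 1 and 2?
- **3.2 and 10.2.1:** affected in the Grade 1–2 laboratory rows, and in the split by attribution, because row 2 turns on relatedness.
- **6.8 stopping triggers:** a related Grade 5 event, or Grade 4 non-hematologic toxicity in 2 or more patients. Neither uses Grade 1–2 records.
- **10.2.1 primary test:** counts sCR and/or MRD-negative responses. Not affected.

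**The case against.** The best defence is context. The section 8 sentence follows an instruction about using CTCAE to describe and grade events, and its subject is events, so it may be meant only for changes in the grade of an AE already identified. Every other text that selects laboratory values applies a filter: the list in section 8 and both sentences in 8.2. Section 8.2 is also the more specific section. On this view one loosely worded sentence stands against three.

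That reading is possible, but the protocol does not state it. Section 8 elsewhere names an abnormal laboratory finding as something that can itself be an AE, and the narrow reading leaves the split within 8.2.

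The second defence is oversight. The coordinating site's CRA trains affiliates on the eCRF (13.5.3), the same institution monitors all sites (13.6), the lead investigator reviews AEs (8.2), and a bi-weekly conference reviews data completeness and validity (13.7). This stands in part: divergence between sites is a risk, not a certainty. It does not supply the missing rule, since monitors would be checking against the same conflicting text.

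Three stronger readings are tempting and should not be drawn.

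- **Sizing by laboratory draws.** Counts and chemistry fall on days 1, 8 and 15 of cycles 1–8 (6.2.2, Appendix 6), so 3 × 8 = 24 draws per subject, and 3 × 4 = 12 for the 15 subjects planned to leave for transplant after cycle 4. These are sampling occasions. Even under section 8 only a change of grade makes a record, and the documents give no rate of such changes. Nor can one assume that 8.2 would capture almost none, because its first sentence admits every Grade 1–2 value judged related.
- **A spoiled comparison with a reference.** The plan makes no AE comparison with historical data; 10.2.1 describes frequencies only.
- **That 8.2 admits only clinically significant values.** It also admits values needing medication or treatment and, in one sentence, related values.

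**Conclusion.** The conflict is real and minor. An untreated Grade 1–2 laboratory shift that is not considered clinically significant is an AE under section 8 and not under the last sentence of 8.2. If judged related, it is recorded under one sentence of 8.2 and excluded under the other. No text says which governs.

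The consequence is limited to Grade 1–2 laboratory AE frequencies in the descriptive safety tables. The size of the shift cannot be stated, because the documents give no rates of low-grade laboratory abnormality. A reader might infer that the safety conclusions as a whole, or trial stopping, are compromised. The documents do not support that, since Grade 3–4 laboratory abnormalities are recorded under every rule and neither the stopping triggers nor the primary test uses the disputed records.

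The conclusion rests on reading the section 8 sentence literally and on taking the and/or in 8.2 as alternatives. Under the narrow reading of section 8, only the inconsistency within 8.2 remains, and it still needs correcting.

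**What to change.** 1. State one recording rule for Grade 1–2 laboratory values, use it in both section 8 and section 8.2, and delete the competing sentences. If the section 8 sentence is meant only for regrading known AEs, say so. Keep the 8.2 rule that every Grade 3–4 laboratory abnormality is recorded as an AE.

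2. In 10.2.1, add a table of worst post-baseline CTCAE grade per subject, derived from all collected laboratory values, scheduled and unscheduled, for the analytes held in the database. It does not depend on which sentence a site followed, so it also helps for data already collected.

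The table should be added to the AE-form summary and not replace it, for three reasons. Derived grades carry no attribution, which 10.2.1 requires. The listed chemistry panel (6.2.2, Appendix 6) has no AST, ALT or calcium, so those still depend on AE forms unless values were otherwise collected. Limiting AE forms to laboratory events needing action would drop Grade 3–4 abnormalities that 8.2 requires. Unscheduled draws must be included because the weekly counts during cytopenia holds (6.6.1.1) may contain the worst grades.

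The cost is wording in 8, 8.2 and 10.2.1, one extra table, and a check that laboratory values are in the study database, since section 8 has them recorded under institutional procedures. Treatment and the primary analysis do not change.

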8.1. Causality

Using the following criteria, the relationship of the AE to the study drug should be assessed as follows:

Definite (5) – The AE is clearly related to the study treatment.

Probable (4) – The AE *is likely related* to the study treatment.

Possible (3) – The AE *may be related* to the study treatment.

Unlikely (2) – The AE *is doubtfully related* to the study treatment.

Unrelated (1) – The AE *is clearly NOT related* to the study treatment.

All AEs will be considered for dose-limiting toxicity evaluation unless the event can clearly be determined to be unrelated to the drug.

8.2. Adverse Event Reporting Procedures

Information about all AEs, whether volunteered by the subject, discovered by the Treating Investigator questioning, or detected through physical examination, laboratory tests or other means, will be collected and recorded in eVelos and followed as appropriate.

All Adverse Events **must** be reported in routine study data submissions to the lead PI who will review and will be responsible for alerting all participating sites about the AE as required. **AEs reported using the Serious Event Reporting Form and/or MedWatch Form discussed below must also be reported in routine study data submissions in eVelos. Details of the event must include severity, relationship to study drug, duration, action taken, and outcome as shown on the eCRF in eVelos. All AEs must be followed to resolution or stabilization regardless of relationship to study drug.**

All AEs that are considered related to study regimen must be followed to resolution or stabilization if improvement is not expected.

AEs must be reported from the date of the first dose of treatment through 30 days post-last dose of study treatment or initiation of a new anti-cancer therapy, whichever occurs first. If a subject is enrolled but discontinues study prior to receiving any study drug, only SAEs that are considered related to study procedures must be reported through the end-of-study visit. AEs that completely resolve and then recur should be recorded as a new AE. For subjects who complete the end of study visit less than 30 days following their last dose of study drug, a follow up of ongoing AEs should be attempted by telephone, and documented in the subject's source. AEs continuing at 30 days post-last dose should have a comment in the source by the Treating Investigator that the event has stabilized or is not expected to improve. SAEs continuing at 30 days post-last dose should be followed until resolution or stabilization.

The Treating Investigator is responsible for evaluating all AEs for relationship to study drug and for seriousness, obtaining supporting documents, and determining that documentation of the event is adequate. Adverse events will be assigned a severity grade using the NCI-CTCAE grading scale v4.0. The Treating Investigator must assess all abnormal laboratory results for their clinical significance. Only grade 1 & 2 abnormal laboratory values considered clinically significant, related to study treatment, and/or requiring concomitant medication will be recorded. If any abnormal laboratory result is considered clinically significant, the Treating Investigator must provide details about the action taken with respect to the test drug and about the subject's outcome. All Grade 3 and 4 laboratory abnormalities must be recorded as AEs on the CRF. Grade 1 and 2 abnormalities should only be recorded if they require treatment or are otherwise considered clinically significant by the Treating Investigator.

The Lead Principal Investigator may delegate these duties to Sub-investigators and must ensure that these Sub-investigators are qualified to perform these duties under the supervision of the Lead Principal Investigator, and that they are listed on the delegation log.

8.3. Serious Adverse Events

All SAEs will be collected by the UC CRA and reviewed by the Lead Principal Investigator. Only those determined to be SUSARs by the Lead Principal Investigator will be distributed to all participating sites (using the completed MedWatch 3500 form). To ensure subject safety, each serious adverse event must be reported to the Lead Principal Investigator and the University of Chicago Comprehensive Cancer Center via paper submission via fax or email within 24 hours of learning of its occurrence. A paper SAE form is provided for this study and may be used and sent via fax or email.

The Lead Principal Investigator is responsible for notifying the investigators of any expedited, annual, or other periodic safety reports in accordance with applicable regulations.

The Site Investigator is also responsible for notifying the local IRB in accordance with local regulations. Additionally, the Lead Principal Investigator is responsible for reporting SAEs to BMS and Amgen as described in section 8.4.

8.3.1. Serious Adverse Event Definition

A Serious Adverse Event (SAE) is any untoward medical occurrence that at any dose:

- Results in death
- Life threatening experience defined as any adverse experience that places the subject, in the view of the Treating Investigator, at immediate risk of death at the time of occurrence; i.e., it does not include a reaction that, had it occurred in a more severe form, might have caused death.
- Requires insubject hospitalization or prolongation of an existing hospitalization (except scheduled hospitalizations for non-acute, unrelated cause such as an elective surgery)
- Results in persistent or significant disability/incapacity or any other medicinal product effects, which the doctor by his state of knowledge deemed serious
- Is a congenital anomaly/birth defect in the offspring of an exposed subject
- Important medical events that may not result in death, be life-threatening, or require hospitalization, may be considered an SAE, when, based upon appropriate medical judgment, it jeopardizes the subject and may require medical or surgical intervention to prevent one of the outcomes listed in this definition.
- Potential drug induced liver injury (DILI) is also considered an important medical event.
- Suspected transmission of an infectious agent (eg, pathogenic or nonpathogenic) via the study drug is an SAE.

Although pregnancy, overdose, and cancer are not always serious by regulatory definition, these events must be handled as SAEs.

Any death occurring within 30 days of the subject receiving study drug, regardless of the subject having discontinued from the study must be reported to the Lead Principal Investigator as an SAE.

ALL Serious Adverse Events MUST be reported to the Lead Principal Investigator and to the University of Chicago Comprehensive Cancer Center (UC CCC), via paper submission via fax or email. This is whether or not they are considered related to the study agent. Refer to Section 8.3.3 for reporting guidelines.

